7.9.2 Individual Stopping Rules

Individuals may stop the study at any time if they experience subjectively intolerable adverse events or dosing symptoms. They must halt up-dosing and re-start with a reduced dose if more than three days of dosing are missed. Seven or more days of missed dosing constitutes an individual stopping rule, as does a significant number of episodes of missed dosing (ie, three or more days on at least three occasions). For additional individual stopping rules, the reader is referred back to Section 4.3.1.

Failure to accomplish up-dosing after three attempts will result in halting further updosing attempts, with the subject maintained at the previously achieved level. In addition, administration of two or more doses of epinephrine for the treatment of doserelated allergic reactions will result in halting further up-dosing attempts, with the subject maintained at the previously achieved level.

8. Mechanistic Assays

Complementary studies will be performed to measure humoral immune responses at baseline and at 6 months.

- Measurement of antigen-specific IgE and IgG4 levels
- SPT to peanut

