- Miss 1 dose The next dose would be the current dose and could be given at home
- Miss 2 doses in a row The next dose would be the current dose and could be given at home
- Miss 3 doses in a row The next dose would be the current dose and would be given under observation (Clinical Research Center)
- Miss 4 doses in a row The next dose would be the current dose and would be given under observation (Clinical Research Center)
- Miss 5-7 doses in a row –Initiate the next dose as approximately 25% of the last tolerated dose. This would be done under observation (Clinical Research Center). Dose escalation would occur in the Clinical Research Center with an escalation no sooner than weekly and no longer than every 4 weeks with dose increases of 1-dose levels at each escalation. If symptoms occur, the dosing symptom rules in the build-up phase would apply
- Missing >7 consecutive days of therapy constitutes an individual stopping rule and the subject would no longer take the study product. The subject will be asked to return to the Clinical Research Center 14 days following their last dose of study product to undergo an Early Discontinuation Visit (see Section 6.5)
- Additionally; excessive missed doses, i.e., > 3 consecutive days missed on 3 occasions, constitutes an individual stopping rule and the subject would no longer take the study product. The subject will be asked to return to the Clinical Research Center 14 days following their last dose of study product to undergo an Early Discontinuation Visit (see Section 6.5).

No attempt should be made to make up for a missed dose if greater than 6 hours have elapsed since usual time of dosing.

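### Protocol Section 7.9.2 conflicts with the Section 6.9 missed-dose algorithm at exactly 4 missed doses and exactly 7 missed days, and states a different repeated-gap threshold

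*Protocol*

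**What the plan says.** Two sections of the protocol tell sites what to do after missed study product.

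**Section 6.9**, the missed-dose algorithm for any phase of the study:
- 1 or 2 missed doses: current dose, may be taken at home.
- 3 missed doses: current dose, observed in the clinic.
- 4 missed doses: "Miss 4 doses in a row The next dose would be the current dose and would be given under observation".
- 5 to 7 missed doses ("Miss 5-7 doses in a row"): "Initiate the next dose as approximately 25% of the last tolerated dose", observed, followed by "escalation no sooner than weekly and no longer than every 4 weeks with dose increases of 1-dose levels".
- Beyond 7: "Missing >7 consecutive days of therapy constitutes an individual stopping rule".
- Repeated gaps: stop after more than 3 consecutive days missed on 3 occasions.

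**Section 7.9.2**, individual stopping rules:
- Restart dose after a gap: "They must halt up-dosing and re-start with a reduced dose if more than three days of dosing are missed".
- Threshold for stopping after one long gap: "Seven or more days of missed dosing constitutes an individual stopping rule".
- Repeated gaps: stop after "three or more days on at least three occasions".

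Two other places bear on the point. Section 4.3.1 (items 6 and 7) uses the same numerical stopping thresholds as 6.9, but under a permissive lead-in, and item 6 covers maintenance dosing only. Section 6.8.2 sends any withheld dose to the missed-dose rules, but numbers them as Section 6.7, which is the Physician Global Assessment. The SAP does not address the matter.

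**The concern.** Dosing is daily, so missed doses and missed days are the same count, and the two sections can be compared directly. At some gap lengths a site cannot obey both. Section 6.9 itself warns that missed doses carry significant risk for subjects, so these are safety rules. With about 8 sites expected (Section 6.1), identical subjects could be restarted at different doses, or stopped in one place and continued in another. At exactly 4 or exactly 7, a site that follows either section departs from the other.

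There is also a secondary link to the primary endpoint. Under Section 9.1.1 and SAP Table 7.1, a subject taken off treatment normally counts as a non-responder in the ITT analysis. A subject stopped at day 7 under 7.9.2 might, under 6.9, still have reached the exit DBPCFC.

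**Working it through.** No plan figure has to be reproduced. The check applies each section to every gap length, reading 7.9.2 as referring to consecutive days (it does not use that word).

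| Gap | Section 6.9 | Section 7.9.2 | Compatible? |
|---|---|---|---|
| 1–2 | current dose, home | no rule | yes |
| 3 | current dose, observed | no rule | yes |
| 4 | current dose, observed | halt up-dosing, reduced dose | **no** |
| 5–6 | about 25%, observed | reduced dose | yes |
| 7 | about 25%, observed | stop | **no** |
| 8 or more | stop | stop | yes |
| three gaps of exactly 3 | stopping rule not triggered | stop | thresholds differ |
| three gaps of 4 or more | stop | stop | yes |

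**Size of the dose difference at 300 mg/day** (dose levels from Table 3-2)
- After 4 missed doses: 6.9 gives 300 mg. Section 7.9.2 gives less, by an unstated amount. If the reduction were one step, the dose would be 240 mg, and 300/240 = 1.25, so the 6.9 dose would be 25% higher.
- After 7 missed days: 6.9 gives 0.25 × 300 = 75 mg (nearest scheduled level 80 mg). Section 7.9.2 gives none.

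**Could the 7-day subject still qualify under 6.9?** From 80 mg the steps are 120, 160, 200, 240 and 300: five increases. At the permitted intervals these take 5 × 1 = 5, 5 × 2 = 10 or 5 × 4 = 20 weeks.

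The documents support two deadlines for regaining 300 mg. Protocol Sections 3.2 and 6.8.4 require it by Week 34, with two maintenance weeks after that. The synopsis, Section 6.13 and the 34-week cap on total dosing in SAP 3.2.2 suggest that the two weeks must fit inside Week 34, so 300 mg is needed by about 34 − 2 = Week 32.

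| Step interval | Latest restart, Week 34 deadline | Latest restart, Week 32 deadline |
|---|---|---|
| weekly | 34 − 5 = 29 | 32 − 5 = 27 |
| 2-weekly | 34 − 10 = 24 | 32 − 10 = 22 |
| 4-weekly | 34 − 20 = 14 | 32 − 20 = 12 |

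SAP 3.2.2 puts first arrival at 300 mg at about Week 18 or 20 when there are no dose reductions. A 7-day gap at 300 mg followed by 4-weekly steps is therefore too late on either deadline. With weekly or 2-weekly steps the choice of section can decide the outcome.

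**Effect on a response rate.** About 50 subjects randomized 1:1 gives about 25 per arm, and 1/25 = 4.0 percentage points per affected subject. This is approximate: with 24 in the arm it is 1/24 = 4.2 points.

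**The case against.** The strongest reply is that 7.9.2 is a loose summary and not an equal rival to 6.9. Section 6.8.2 refers by name to the missed-dose rules, and only 6.9 carries that title, so the wrong section number hardly obscures the target. Section 4.3.1, to which 7.9.2 itself sends the reader for further stopping rules, repeats the 6.9 thresholds. This stands: 6.9 is evidently meant to govern, and a reader who infers that the protocol gives no guidance goes too far. It does not remove the conflict. Section 7.9.2 is worded as mandatory and refers to 4.3.1 only for additional rules. Section 4.3.1 is permissive and silent on the restart dose after 4 missed doses.

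A reader might also infer that the repeated-gap rules contradict each other as directly as the other two. They do not. The triggers are nested: stopping at 3 or more days also satisfies stopping at more than 3. No text obliges a site to continue a subject with three 3-day gaps, and item 11 of 4.3.1 lets the investigator stop for safety. This is a threshold inconsistency.

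Observed restart dosing under 6.9 and access to the Medical Monitor soften the risk. But the Monitor is offered in 6.8.2 for dosing questions that the protocol leaves unanswered. Here each section gives an apparently complete answer, so a site reading one has no reason to ask.

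**Conclusion.** The protocol is wrong as written at exactly 4 missed doses and at exactly 7 missed days, and it states two different repeated-gap thresholds. Section 6.9 has the clearly better claim, but nothing says that it overrides 7.9.2. The main consequence is inconsistent restart and stopping decisions on a safety matter, and it should be fixed.

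The endpoint effect is secondary: roughly 4 points in one arm per affected subject, and only where the timing and re-escalation interval leave room to qualify. The mITT sensitivity analysis (SAP 5.5) would exclude such a subject if the withdrawal were judged unrelated to treatment success or failure. A reader might infer bias between arms or a threat to the primary result. The documents do not support that, since they give no expected frequency of such gaps and no reason for them to differ by arm.

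The conclusion assumes that 7.9.2 means consecutive days. Taken literally it could count cumulative missed days, which would widen the conflict, but the documents do not establish that this is intended. The latest-restart weeks depend on whether 300 mg is needed by Week 34 or Week 32, which the documents leave open.

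**What to change.** Replace the missed-dose sentences in 7.9.2 with a cross-reference to 6.9, so that one rule applies throughout:
- 4 missed doses: current dose under observation.
- 5 to 7: restart at about 25% of the last tolerated dose, under observation.
- More than 7 consecutive days, or more than 3 consecutive days on 3 or more occasions: stop.

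Correct the pointer in 6.8.2 from Section 6.7 to Section 6.9. Align items 6 and 7 of 4.3.1 with the mandatory, any-phase rule in 6.9.

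If the sponsor prefers the stricter 7.9.2 limits on safety grounds, change 6.9 and 4.3.1 instead, and state the size of the dose reduction after 4 missed doses.

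Cost: a wording-only protocol amendment. Under Section 11.1 it needs sponsor, DMC and IRB approval and submission to FDA before use. It needs no extra visits, data or subjects.

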8.1 Peanut-Specific Antibody

Antigen immunotherapy has been shown to induce antigen-specific humoral responses. The balance of isotypic response may play a role in allergen sensitivity (e.g., an increase of IgG/ IgE).

At each of the mechanistic time points, a sample of plasma will be stored for assessment of peanut specific antibody levels. Total IgE and specific IgE and IgG4 will be measured using UniCAP. Peanut specific IgE and IgG4 blood draws will be measured at screening and at Visit 03, with the amount of blood to be drawn determined by individual laboratory protocol.

9. Statistical Considerations

This protocol is a randomized evaluation of peanut OIT versus placebo therapy and baseline for individuals with peanut allergy.

9.1 Study Endpoint Assessment

9.1.1 Primary Endpoint

The primary endpoint is the proportion of subjects who achieve desensitization as determined by tolerating at least 300 mg (443 mg cumulative) of peanut protein with no more than mild symptoms at the exit DBPCFC (ie, responders).

Those who fail to achieve the target maintenance dose of at least 300 mg of study product will be considered as non-responders. An intent-to-treat analysis will be performed to test for a treatment difference in the response rate. All individuals failing to achieve the success definition described above will be considered failures. All individuals who drop out of the study or discontinue OIT will be considered failures, unless they have added *ad libitum* peanut consumption to their diet otherwise. Analysis will be via Chi-square test at the 0.05 significance level.

9.1.2 Secondary Endpoints

The secondary endpoints are defined in Section 3.7.

9.2 Subject and Demographic Data

9.2.1 Baseline Characteristics and Demographics

Summary descriptive statistics for baseline and demographic characteristics will be provided for all enrolled subjects. Demographic data will include age, race, sex, body weight and height; these data will be presented in the following manner:

- Continuous data (i.e., age, body weight and height) will be summarized descriptively by mean, standard deviation, median and range.
- Categorical data (i.e., sex and race) will be presented as enumerations and percentages.

Statistical presentation for baseline and demographic characteristics may be further summarized by treatment group and baseline peanut-specific serum IgE.

9.2.2 Use of Medications

All medications used will be coded using the World Health Organization (WHO) drug dictionary. The number and percentage of subjects receiving concomitant medications or therapies will be presented. Statistical presentation of concomitant medications or therapies may be further summarized by treatment group.

9.2.3 Study Completion

The percent of subjects who complete the study, losses to follow-up, times to lost to follow-up and reasons for discontinuation (e.g., adverse events) will be presented. Statistical presentation of study completion will be further presented via analysis of the secondary endpoints summarized.

9.3 Sample Size and Power Calculations

While natural history of peanut allergy desensitization is not fully understood, significant short-term improvements in consumption amounts are believed to be uncommon. A true placebo response rate of 25% or less among subjects who undergo the exit DBPCFC is assumed in this study. Those individuals who fail to achieve the target daily dose or who withdraw prematurely will be treated as non-responders. We will recruit approximately 50 subjects.

If 3 subjects in each arm (about 12%) do not undergo the exit DBPCFC, then the effective placebo response rate in the ITT analysis is assumed to be 22% or less. With a 2-tailed 5% level test, there is at least 80% power to detect an effective CPNA response rate of 58.7% or more, which corresponds to a CPNA response rate of 66.7% or more among those who undergo the exit DBPCFC.

If 5 subjects in each arm (about 20%) do not undergo the DBPCFC, then the effective placebo response rate in the ITT analysis is assumed to be 20% or less. With a 2-tailed 5% level test, there is at least 80% power to detect an effective CPNA response rate of 56.6% or more, which corresponds to a CPNA response rate of 70.75% or more among those who undergo the exit DBPCFC.

10. Identification and Access to Source Data

10.1 Web-Based Data Collection and Management System

Data collection will occur via a web-based data entry system to allow easy access to enrollment 24 h a day, 7 days a week. Upon enrollment, a form submission schedule is generated for each subject and displayed as a grid of forms by study visit that permits direct access to each electronic CRF for data entry. As data are entered, they are validated through range and within-form consistency checks. The investigator must ensure that all web-based CRFs are completed in a timely fashion for each subject in the study.

10.2 Certification in the Use of Web-Based Data Entry System

The clinic and laboratory staff will be trained in the use of the data entry and specimentracking systems. Once certified, users are permitted to enter data into the production system. Access is password controlled. Certification for use of the web-based data entry system will be completed via telephone and/or web-cast training.

10.3 Data Management

Information regarding the subject's history, laboratory tests, nutritional intake, evaluation of allergic response and follow-up status will be stored and processed through the data center. Quality control procedures and a feedback system between the data center and the sites will be instituted to ensure the accuracy and completeness of the data collected.

10.4 Access to Data

The investigational sites shall periodically permit authorized representatives of the IND sponsor, and/or regulatory health authorities to examine clinical records and other source documents for the purpose of safety monitoring, quality assurance reviews, audits and evaluation of the study progress throughout the entire study period. The investigator is required by law (21 CFR 312.62) to keep accurate case records for at least 2 years after acceptance of a licensure application and FDA is notified, and record observations to assure the safe conduct of the study.

11. Quality Control and Quality Assurance

11.1 Statement of Compliance

This study will be conducted using good clinical practice (GCP), as delineated in the United States Code of Federal Regulations (CFR) – 21 CFR Parts 50, 54, 56 and 312 and in the International Conference on Harmonisation of Technical Requirements for Registration of Pharmaceuticals for Human Use (ICH) "Guidance for Industry: E6 Good Clinical Practice Consolidated Guidance", and according to the criteria specified in this study protocol. Before study initiation, the protocol and the informed consent documents will be reviewed and approved by an appropriate IRB as well as FDA. Any amendments to the protocol or must also be approved by the sponsor, DMC, IRB and submitted to the

FDA before they are implemented. Any amendments to the consent materials must also be approved by the sponsor and IRB before they are implemented.

11.2 Informed Consent/Assent

The informed consent form is a means of providing information about the study to a prospective subject's parent/guardian and allows for an informed decision about participation in the study. Because the study population will be comprised of a significant percentage of children, parents or legal guardians will be asked to read, sign and date a consent form before a child enters the study, takes study product, or undergoes any study-specific procedures. Children will sign an assent as appropriate. Consent materials for parents/guardians who do not speak or read English will be translated into the appropriate language. The informed consent form will be given to a prospective parent/guardian for review. The attending physician, in the presence of a witness, will review the consent and answer questions, as well as emphasize the need to avoid allergen exposure other than to Characterized Peanut Allergen, and the necessity to continue exposure to Characterized Peanut Allergen to maintain de-sensitization. The prospective parent/guardian will be told that being in the study is voluntary and that he or she may withdraw his/her child from the study at any time, for any reason.

11.3 Privacy and Confidentiality

A subject's privacy and confidentiality will be respected throughout the study. Each subject will be assigned a sequential identification number and these numbers rather than names will be used to collect, store and report subject information.

12. Resource Sharing

All data derived from this study will be sent to the Coordinating Center for storage and analysis. Subject data will be anonymized to maintain subject confidentiality. All data derived from these studies will be published in peer-reviewed scientific journals in a timely manner. The sponsor will review all manuscripts prior to submission to journals for publication and all abstracts prior to submission to national and international meetings. All data sets will be archived by the Coordinating Center and may be made available to interested, outside investigators with the approval by the sponsor.

13. Protocol Deviations

The investigators and site staff will conduct the study in accordance to the protocol. Any change, divergence, or departure from the study design or procedures constitutes a protocol deviation. Whenever applicable, corrective actions will be developed by the site and implemented promptly as a result of protocol deviations.

13.1 Major Protocol Deviation (Protocol Violation)

A Protocol Violation is a deviation from the IRB approved protocol that may affect the subject's rights, safety, or well-being and/or the completeness, accuracy and reliability of the study data. In addition, protocol violations include willful or knowing breaches of

human subject protection regulations, or policies, any action that is inconsistent with medical, and ethical principles, and a serious or continuing noncompliance with federal, state, local or institutional human subject protection regulations, policies, or procedures.

13.2 Non-Major Protocol Deviation

A non-major protocol deviation is any change, divergence, or departure from the study design or procedures of a research protocol that does not have a major impact on the subject's rights, safety or well-being, or the completeness, accuracy and reliability of the study data.

Appendix 1: Schedule of Events

	Screening	Blinded Treatment				Exit/Early Discontinuation
Procedure	Visit 00 Screening	Baseline Visit	Visit 01 Initial Escalation (Day 1-3) ¹	Up-dosing visits (approx. every 2 wks for 24 wks) ²	Visit 02 (approx. 12 wks)	Visit 03
Informed consent	Х	Х				
Inclusion/exclusion criteria	Х	Х				
Medical/allergy history	Х	Х			Х	Х
Concomitant medications	Х	Х	Х	Х	Х	Х
Physical exam, including weight and height	Х	Х	Х	Х	Х	Х
Vital signs (BP, PR, temperature)	Х	Х	Х	Х	Х	Х
Peak flow rate (PEFR) ³	Х	Х	Х	Х	Х	Х
Pregnancy test ⁴	X serum	X urine			X urine	X urine
Diet history	Х		Х		Х	Х
Blood draw for peanut specific IgE, IgG4	Pre- DBPCFC					Pre-DBPCFC
Optional blood draw for ITN	Pre- DBPCFC					Pre-DBPCFC
analysis ⁵	5-10 da DBP	ys post- CFC				
Skin prick test	Х					Х
Clinical Research Center study product administration			Х	Х	Х	Х
Dispensing study products for home dosing/Return of unused products			Х	Х	Х	
Physician Global Assessment		Х				Х
Dose assessment to decide for maintenance or up- dosing						Х

	Screening	Blinded Treatment				Exit/Early Discontinuation
Procedure	Visit 00 Screening	Baseline Visit	Visit 01 Initial Escalation (Day 1-3) ¹	Up-dosing visits (approx. every 2 wks for 24 wks) ²	Visit 02 (approx. 12 wks)	Visit 03
Double-blind, placebo controlled food challenge (DBPCFC) PRACTALL guidelines	Х					X ⁶
Telephone monitoring of dosing compliance and symptoms ⁷			X 1 wk after visit	Х	Х	Х
Adverse events ⁸			Х	Х	Х	Х

1. Visit 01: Escalation to at least 3.0 mg on Day 1, return Day 2, return Day 3 if symptoms present, return for dose escalation every 2 weeks. Dose escalation schedule is shown in Table 3-1.

2. Up-dosing visits: every 2 .weeks at clinic, unless epinephrine is administered as described in Section 6.8. Dose escalation schedule is shown in Table 3-1

3. Prior to any DBPCFC and at Baseline; 3 attempts, best value taken; should be measured at the same time for each visit assessment

4. For females of childbearing potential

5. For subjects \geq 30kg only, at 5 mL/kg, with a maximum of 60 mL in total; analysis by ITN.

6. Eligible subjects (up-dose to 300 mg plus 2 weeks on 300 mg) only will undergo a DBPCFC at the exit visit.

7. Phone calls will occur 1 week after each escalation visit to assess dosing compliance and symptoms. Schematic for symptoms is described in Figure 6–1 and Figure 6–2.

8. AEs will be evaluated from the onset until the event is resolved or medically stable, or until 30 days after the subject completes study treatment, whichever comes first.

